3.11.3.1.3. Month 6 (Visit 6)

The following procedures/assessments will be performed at Month 6 (Visit 6):

- Review of concomitant medications
- Adverse events inquiry
- perform full physical examination (including weight)
- perform vital signs measurements
- perform single ECG
- perform clinical laboratory tests
- estimated creatinine clearance calculation
- clinical hematology
- thyroid function (T3, T4, TSH)
- blood sample for soluble biomarkers (cytokines)
- blood sample for gene expression analysis
- serum β -HCG in women of child-bearing potential
- urine β -HCG in women of child-bearing potential
- Ascertaining use of acceptable contraception
- C-SSRS (since last visit version)
- UHDRS-TMS
- UHDRS-TFC
- UHDRS-FA

- mPPT
- CIBIC-plus
- Q-Motor assessments
- HD-CAB
 - Includes Symbol Digit Modalities Test (SDMT), Emotion Recognition, Trail Making Test, Hopkins Verbal Learning Test, revised (HVLTR), Paced Tapping at 3 Hz, One Touch Stockings of Cambridge (OTS, abbreviated 10 trial version)
- PK drug concentration sampling
- Review study compliance
- Study drug collection and reconciliation
- Study drug dispensing

3.11.3.1.4. Month 9 (Visit 7)

The following procedures/assessments will be performed at Month 9 (Visit 7):

- Review of concomitant medications
- Adverse events inquiry
- perform full physical examination (including weight)
- perform vital signs measurements
- perform clinical laboratory tests
- estimated creatinine clearance calculation
- clinical hematology
- serum β -HCG in women of child-bearing potential
- urine β -HCG in women of child-bearing potential
- Ascertaining use of acceptable contraception
- C-SSRS (since last visit version)
- Review study compliance
- Study drug collection and reconciliation
- Study drug dispensing

3.11.3.1.5. Month 12 (Visit 8) –or Early Termination

The following procedures/assessments will be performed at Month 12 (Visit 8) or early termination:

- Review of concomitant medications
- Adverse events inquiry
- perform full physical examination (including weight)
- perform vital signs measurements
- perform single ECG
- perform clinical laboratory tests
- estimated creatinine clearance calculation
- clinical hematology
- lipid profile
- thyroid function (T3, T4, TSH)

- blood sample for soluble biomarkers (cytokines)
- blood sample for gene expression analysis
- blood sample for monocyte analysis (**Only at selected sites in a subgroup of patients**)
 - Blood sample for monocyte collection and analysis has to be done in accordance with the laboratory manual
 - For UK patients, the sample can be drawn prior to the Month 12 visit, as it coincides with the PET scan visits
- serum β -HCG in women of child-bearing potential
- urine β -HCG in women of child-bearing potential
- additional urine β -HCG in women of child-bearing potential at PET facilities (**Only in a subgroup of patients**)
- Ascertaining use of acceptable contraception
- PK drug concentration sampling
- C-SSRS (since last visit version)
- MRI scan
 - If anxiolysis is required in order to perform the MRI scan, the scan should be performed at the end of the study visit day.
- MRS scan (**Only at selected sites in a subgroup of patients**)
- PET scan (**Only in a subgroup of patients**)
 - The PET scan can be done 2 to 5 weeks prior to the Month 12 visit.
 - Patients taking benzodiazepines should be instructed to stop taking them for 3 days prior to having the PET scan.
- UHDRS-TMS
- UHDRS-TFC
- UHDRS-FA
- mPPT
- PBA-s
- CIBIC-plus
- HD-QoL
- EQ-5D-5L
- WLQ
- Q-Motor assessments
- HD-CAB
 - Includes Symbol Digit Modalities Test (SDMT), Emotion Recognition, Trail Making Test, Hopkins Verbal Learning Test, revised (HVLRT-R), Paced Tapping at 3 Hz, One Touch Stockings of Cambridge (OTS, abbreviated 10 trial version)
- CDR-SB
- HADS
- Review study compliance
- Study drug collection and reconciliation

Moderate/strong CYP3A4 inhibitors are disallowed during the 30 days after the last laquinimod dose has been administered (see [Appendix B](#)).

Plasma levels of drugs that are CYP1A2 substrates may decrease when combined with laquinimod and within 30 days after the last laquinimod dose, rendering these drugs less effective (see [Appendix C](#)).

Early termination refers to the study drug termination and not termination of the patient from the study. Patients in the 1.5 mg/day (high dose) treatment arm, whose treatment with laquinimod was discontinued, were invited to attend an early termination safety visit to return study medication and perform drug accountability. At this visit, only safety assessments (vital signs, clinical laboratory tests, pregnancy test, adverse event inquiry, drug accountability, review of concomitant medication, and C-SSRS) were to be conducted (see Section [3.6.2](#)), and none of the efficacy assessments. Patients were asked to continue all scheduled visits for safety assessment after study drug discontinuation.

Patients in the high dose group (1.5mg/day) who were requested to discontinue study drug before week 52, but who continue to attend scheduled study visits for safety assessment, are not considered to have completed the study.

3.11.4. Procedures After Study Drug Treatment

3.11.4.1. Follow-Up (Week 56, Visit 9)

The following procedures/assessments will be performed at the follow up visit (Week 56, Visit 9):

- Review of concomitant medications
- Adverse events inquiry
- perform clinical laboratory tests
- estimated creatinine clearance calculation
- clinical hematology
- perform full physical examination (including weight)
- perform vital signs measurements
- perform single ECG
- serum β -HCG in women of child-bearing potential
- urine β -HCG in women of child-bearing potential
- Ascertaining use of acceptable contraception
- C-SSRS (since last visit version)

Patients who participate in the study in compliance with the protocol for the entire duration of the double-blind treatment will be considered to have completed the study.

For patients who complete the study or withdraw prematurely, final evaluations will be performed at the end-of-treatment visit or as soon as possible thereafter. Procedures for patients who withdraw prematurely from the study are described in Section [4.3](#).

If it is not possible to schedule the ET visit within 2 weeks after end of treatment, only the safety evaluations for that visit (vital signs, clinical laboratory tests, pregnancy test, adverse event

inquiry, drug accountability, review of concomitant medication, and C-SSRS, see Section 3.6.2) need to be performed.

Patients with ongoing adverse events or clinically significant abnormal laboratory test results (as interpreted by the investigator) will be monitored as described in Section 7.1.2 and Section 7.3, respectively.

3.11.5. Unscheduled Visits

An unscheduled visit may be performed at any time during the study at the subject's request or as deemed necessary by the investigator. The date and reason for the unscheduled visit will be recorded on the CRF as well as any other data obtained (e.g., adverse events, concomitant medications and treatments, and results from procedures or tests).

Mandatory Unscheduled Visit Procedures (except for subjects that perform the unscheduled visit for repeat MRI scan):

- Vital signs
- Evaluation of AEs
- Review of concomitant medications
- Review of study drug accountability
- Compliance
- Ascertaining use of acceptable contraception

Other procedures may be performed at the discretion of the investigator, and must be recorded in the source documentation.

According to the judgment of the investigator or medical monitor, the following unscheduled procedures may be performed:

- urgent safety laboratory test panel (see Section 7.3.4)
- estimated creatinine clearance calculation
- collection of unscheduled pharmacokinetic blood sample
- collection of sample for potential biomarker analysis

4. SELECTION AND WITHDRAWAL OF PATIENTS

4.1. Patient Inclusion Criteria

Patients may be included in the study only if they meet all of the following criteria:

- a. **[New criterion]** Documentation of prior positive genetic testing for HD, or a clinical diagnosis of symptomatic HD (Diagnostic Confidence Level 4).
- b. **[Revision 1]** Presence of 36-49 CAG repeats, inclusive, in the huntingtin gene based on centralized CAG testing during screening.
- c. Male or female between 21-55 years of age, inclusive, with an onset of HD at or after 18 years of age.
- d. **[Revision 1]** Women of child-bearing potential (women who are not post menopausal or who have not undergone surgical sterilization) must practice an acceptable method of birth control for 30 days before taking the study treatment, and 2 acceptable methods of birth control during all study duration and until 30 days after the last dose of treatment was administered. Acceptable methods of birth control in this study include: Intrauterine device, barrier method (condom or diaphragm with spermicide) and hormonal methods of birth control (e.g., oral contraceptive, contraceptive patch, long-acting injectable contraceptive).
- e. A sum of >5 points on the UHDRS-TMS at the screening visit
- f. UHDRS-TFC \geq 8 at the screening visit.
- g. Able and willing to provide written informed consent prior to any study related procedure being performed at the screening visit. Patients with a legal guardian should be consented according to local requirements.
- h. Willing to provide a blood sample for genomic CAG analysis at the screening visit.
- i. Willing and able to take oral medication and able to comply with the study specific procedures.
- j. Ambulatory, being able to travel to the study centre, and judged by the investigator as likely to be able to continue to travel for the duration of the study
- k. Availability and willingness of a caregiver, informant, or family member to provide input at study visits assessing CIBIC-Plus, CDR-SB, PBA-s and HD-QoL. A caregiver is recommended to be someone who attends to the patient at least 2 to 3 times per week for at least 3 hours per occasion, and the suitability of the caregiver should be judged by the investigator.
- l. For patients taking allowed antidepressant medication, the dosing of medication must have been kept constant for at least 30 days before baseline and must be kept constant during the study.

4.2. Patient Exclusion Criteria

Patients will be excluded from participating in this study if they meet any of the following criteria:

- a. Use of immunosuppressive agents, or cytotoxic agents, including cyclophosphamide and azathioprine within 12 months prior to screening
- b. Previous use of laquinimod
- c. Use of moderate/strong inhibitors of CYP3A4 within 2 weeks prior to randomization.
- d. Use of inducers of CYP3A4 within 2 weeks prior to randomization.
- e. Pregnant or breastfeeding.
- f. **[Revision 1]** Serum levels $\geq 2 \times \text{ULN}$ of either ALT or AST at screening.
- g. **[Revision 1]** Serum direct bilirubin which is $\geq 1.5 \times \text{ULN}$ at screening.
- h. **[Revision 2]** Estimated creatinine clearance < 60 mL/min at screening, calculated using the Cockcroft Gault equation:
 $(140 - \text{age}) \times \text{mass (kg)} \times [0.85 \text{ if female}] / 72 \times \text{serum creatinine (mg/dL)}$
- i. **[Revision 1]** Subjects with a clinically significant or unstable medical or surgical condition that may put the patient at risk when participating in the study or may influence the results of the study or affect the patient's ability to take part in the study, as determined by medical history, physical examinations, ECG, or laboratory tests. Such conditions may include:
 1. A major cardiovascular event (e.g. myocardial infarction, acute coronary syndrome, de-compensated congestive heart failure, pulmonary embolism, coronary revascularization, angina) that occurred prior to randomization.
 2. Significant cardiovascular risk factors (such as, but not limited to, uncontrolled hypertension, uncontrolled diabetes), per investigator discretion.
 3. Any acute pulmonary disorder
 4. A CNS disorder other than HD that may jeopardize the subject's participation in the study, including such disorders that are demonstrated on the baseline MRI (based on local read).
 5. A gastrointestinal disorder that may affect the absorption of study medication.
 6. Acute or chronic renal disease including acute kidney injury (AKI).
 7. Any form of acute or chronic liver disease.
 8. Known human immunodeficiency virus positive status. Patients will undergo an HIV test at screening per local requirements, if applicable.
 9. Any malignancies, excluding basal cell carcinoma, in the 5 years prior to randomization.

- j. Any clinically significant, abnormal, screening laboratory result which in the opinion of the investigator, affects the patients' suitability for the study or puts the patient at risk if he/she enters the study
- k. Unsuitable for MRI (e.g., claustrophobia, metal implants)
- l. Alcohol and/or drug abuse within the 12 months prior to screening, as defined by Diagnostic and Statistical Manual of Mental Disorders – Fourth Edition Text Revision (DSM-IV TR) criteria for substance abuse. For former alcohol and/or drug abusers, the abstinence should be confirmed by laboratory tests (drug testing and/or carbohydrate deficient transferrin (CDT) level in blood).
- m. Patients with active suicidal ideation during the past month as measured by a most severe suicide ideation score of 4 (Active Suicidal Ideation with Some Intent to Act, without Specific Plan) or 5 (Active Suicidal Ideation with Specific Plan and Intent) on the baseline screening Columbia-Suicide Severity Rating Scale (C-SSRS) or subjects who answer "Yes" on any of the 5 C-SSRS Suicidal Behavior Items (actual attempt, interrupted attempt, aborted attempt, preparatory acts, or behavior) if the attempt or acts were performed within 1 year of screening, or subjects who, in the opinion of the investigator, present a serious risk of suicide.
- n. Patients with known intracranial neoplasms, vascular malformations, or intracranial hemorrhage
- o. Known drug hypersensitivity that would preclude administration of laquinimod or placebo, such as hypersensitivity to mannitol, meglumine or sodium stearyl fumarate.
- p. Swallowing difficulties that would preclude administration of laquinimod or placebo capsules.
- q. [Revision 1] Treatment with any investigational product within 30 days of screening or patients planning to participate in another clinical study assessing any investigational product during the study. Patients in non-interventional and/or observational studies will not be excluded from participating in this study.
- r. Treatment with tetrabenazine within 30 days of the study baseline visit
- s. Treatment with antipsychotic medication within 30 days of the study baseline visit

4.3. Withdrawal Criteria and Procedures

In accordance with the Declaration of Helsinki (in accordance with the applicable country's acceptance), each patient is free to withdraw from the study at any time. The investigator also has the right to withdraw a patient from the study in the event of intercurrent illness, adverse events, pregnancy (see Section 7.3.3), or other reasons concerning the health or well-being of the patient, or in the event of lack of cooperation. In addition, a patient may be withdrawn from the study as described in Sections 3.6, 3.8, 3.11.4, 5.4, and 7.1.7.

Specific safety reasons for withdrawing a patient from the study are described in detail in [Appendix A](#) and Section 3.6. These include:

- Elevated liver enzymes (as detailed in [Appendix A](#))
- Pregnancy

- Need for concomitant treatment with moderate and strong CYP3A4 inhibitors
- Patients that are diagnosed with a malignant solid or liquid tumor
- Acute coronary syndrome, myocardial infarction or any major cardiovascular event

Should a patient decide to withdraw after administration of study drug(s), or should the investigator decide to withdraw the patient, all efforts will be made to complete and report all observations up to the time of withdrawal. A complete final evaluation at the time of the patient's withdrawal (including all Visit 8 procedures) should be made and an explanation given as to why the patient is withdrawing or being withdrawn from the study.

The reason for and date of withdrawal from the study must be recorded on the source documentation and transcribed onto the CRF. If a patient withdraws consent, every attempt will be made to determine the reason. If the reason for withdrawal is an adverse event or a clinically significant abnormal laboratory test result, monitoring will be continued at the discretion of the investigator (e.g., until the event has resolved or stabilized, until the patient is referred to the care of a health care professional, or until a determination of a cause unrelated to the study drug or study procedure is made). The specific event or test result(s) must be recorded on the source documentation and transcribed onto the CRF.

All evaluations should be performed according to the protocol on the last day the patient takes study drug, or as soon as possible thereafter. If it is not possible to schedule the ET visit within 2 weeks after end of treatment, only the safety evaluations for that visit need to be performed.

For patients in the 1.5 mg arm who were withdrawn from study treatment, the reason will be recorded as 'sponsor requested patient to be withdrawn'.

5. TREATMENT OF PATIENTS

5.1. Study Drugs Administered

Until 10 January 2016, at the baseline visit, patients were randomly assigned in a 1:1:1:1 ratio to 1 of 3 laquinimod treatment groups or to the placebo treatment group. Three capsules will be administered orally once each day, at the same time of the day, as follows:

- Oral laquinimod 0.5 mg: 3 capsules, 1 containing 0.5 mg laquinimod and 2 capsules containing matching placebo, to be administered orally qd.
- Oral laquinimod 1.0 mg: 3 capsules, 2 containing 0.5 mg laquinimod and 1 capsule containing matching placebo, to be administered orally qd.
- Oral laquinimod 1.5 mg: 3 capsules containing 0.5 mg laquinimod (Note: The treatment of this high dose arm was discontinued as of 10 January 2016)
- Matching placebo: 3 capsules, containing 0.5 mg matching placebo, to be administered orally qd.

As of 10 January 2016, following the decision to discontinue treatment of the laquinimod 1.5 mg dose arm, additional eligible patients who are enrolled will be randomized in a 1:1:1 ratio to receive laquinimod 0.5 mg/day, 1.0 mg/day, or matching placebo for 52 weeks.

The capsules will be taken orally and must be swallowed whole with a glass of water. The capsule should not be opened. Laquinimod can be taken with or without food.

The time of the dosing will be recorded on the CRF.

Compliance to study drug administration will be monitored. See Section 5.4 for additional information.

Study drug will be packaged in bottles and provided for patients to take at home (see Section 3.4). Study drug exposure will be measured and compliance to study drug administration will be monitored.

5.2. Restrictions

There are no restrictions in this study.

However, regarding fasting prior to in-clinic visits that will require fasting blood draws:

For visits 2 through 9, patients must have fasted (no food or beverages) no less than 8 hours prior to each morning visit that will require fasting blood draws (i.e. a blood draw for the lipid profile, or for the safety laboratory panels which include clinical chemistries and hormone concentrations).

Patients will be permitted to have water up until 1 hour before blood draws.

For patients participating in the PK-profiling ancillary study, the fasting conditions will be held up to 4 hours after the dosing.

5.3. Prior and Concomitant Therapy or Medication

Any prior or concomitant therapy, medication, or procedure a patient has had within 3 months before study drug administration and up to the end of the study period, including follow-up, will be recorded on the CRF. Generic or trade name, indication, and dosage will be recorded. The sponsor will encode all therapy and medication according to the World Health Organization (WHO) drug dictionary (WHO Drug).

At each clinic visit after the screening visit, the investigator will ask patients whether they have taken any medications (other than study drug), including over-the-counter (OTC) medications, vitamins, or herbal or nutritional supplements, since the previous visit. Indication, dosage, and start and end dates should be entered on the CRF.

5.3.1. Disallowed Previous Medications/Therapies Prior to and During the Study

The following medications will not be allowed prior to and during this study:

- Use of tetrabenazine within 30 days prior to baseline and during the study;
- Use of antipsychotic medication within 30 days prior to baseline and during the study;
- Use of moderate/strong inhibitors of CYP3A4, such as erythromycin and ketoconazole (more examples listed in [Appendix B](#)), within 2 weeks prior to randomization, during the study and until 30 days after the last study dose has been administered. Laquinimod is extensively metabolized predominantly by CYP3A4, and ketoconazole and fluconazole, strong and moderate inhibitors of CYP3A4, were found to inhibit the metabolism, leading to 2.5- and 3.1-fold increases in laquinimod exposure, respectively.
- Use of inducers of CYP3A4 within 2 weeks prior to randomization and during the study;
- Immunosuppressive or immunomodulating agents, or cytotoxic agents, including cyclophosphamide and azathioprine within 12 months prior to screening and during the study;
- Use of experimental or investigational drugs and/or participation in drug clinical studies within 30 days of screening and during the study.

For patients taking antidepressant medication, the dose has to be kept constant for at least 30 days prior to randomization and during the whole study period.

[Appendix B](#) provides a list of medications disallowed prior to and during the study.

Patients who for their safety and well-being, according to the treating physician, are in need of antipsychotic medication or changed dose of antidepressant medication during the study, will be allowed to continue in the study, and the change in concomitant medication will be recorded in the CRF.

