1.7. Population To Be Studied

Based on the anticipated mode of action (MoA) of laquinimod in HD, an intervention to reduce CNS inflammation as early as possible would be desirable to prevent further neuronal dysfunction and death. However, the rate of progression in signs and symptoms makes it difficult to detect slowing of disease in a feasible way in terms of treatment length in patients without signs of disease. Therefore, patients with clinical symptoms that are measurable, but with a retained functional capacity will be selected. Further, concomitant medications with antipsychotic drugs may confound the data due to side effects in the motor and cognitive domain, and thus these drugs will be disallowed in the study. It is also known that cytosine-adenosine-guanine (CAG) repeat length in the mutant huntingtin gene influence disease progression and course. To reduce variability in the study, patients will be selected from a pre-defined range of CAG repeat lengths frequently observed in the clinic.

Thus, the target patient population will be adult patients, with a CAG repeat length between 36 and 49, and the basic eligibility criteria will select a patient population with symptoms of HD, as assessed by a Unified Huntington's Disease Rating Scale Total Motor Score (UHDRS-TMS) >5 , but with a largely retained functional capacity, as assessed with a HDRS-Total Functional Capacity (UHDRS-TFC) score ≥ 8 . This will recruit a symptomatic early HD patient population.

The criteria for study eligibility are described in Section 4.1 and Section 4.2, respectively.

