7.1.7. Withdrawal Due to an Adverse Event

Any patient who experiences an adverse event may discontinue treatment at any time at the discretion of the investigator. If a patient discontinues treatment wholly or in part because of an adverse event, both the adverse events page and termination page of the CRF will be completed at that time.

A complete final evaluation at the time of the patient's withdrawal (Visit 8 procedures) should be made. In addition, a blood sample will be obtained for the measurement of study drug concentrations. The patient will be monitored at the discretion of the investigator (e.g., until the event has resolved or stabilized, until the patient is referred to the care of a health care professional, or until a determination of a cause unrelated to the study drug or study procedure is made). The investigator must inform the clinical project physician/clinical leader (CPP/CL) as soon as possible of all patients who are being considered for withdrawal due to adverse events. Additional reports must be provided when requested.

If a patient discontinues treatment for multiple reasons that include adverse events, the termination page of the CRF should indicate that the withdrawal was related to an adverse event.

An exception to this requirement will be the occurrence of an adverse event which in the opinion of the investigator is not severe enough to warrant discontinuation but which requires the use of a prohibited medication, thereby requiring discontinuation of the patient. In such a case, the reason for discontinuation would be need to take a prohibited medication, not the adverse event.

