9.6.2.1. Primary Efficacy Endpoint Analysis

The change from baseline in UHDRS-TMS, will be analyzed using a Repeated Measures model (SAS® MIXED procedure with REPEATED sub-command). The model will include the following fixed effects: categorical week in trial by treatment interaction, center, and UHDRS-TMS at baseline. The unstructured covariance matrix for repeated observations within patients will be used. In case that the model will not converge, the Maximum-Likelihood (ML) estimation method will be used instead of the default Restricted ML (REML). If the model still does not converge then a simpler covariance structures with less parameters will be used, according to the following order: Heterogeneous Autoregressive(1) [ARH(1)], Heterogeneous Compound Symmetry (CSH), Autoregressive(1) [AR(1)], and Compound Symmetry (CS). The estimated mean changes from baseline at the Month 12//Early Termination visit will be compared between the active treatment arms and the placebo arm.

The Hochberg's Step-Up method for multiple comparisons between treatment arms will be used to control inflation in type I error rate.

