9.6.2.4. Sensitivity Analysis

No sensitivity analyses are planned for this study.

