9.8.2. Safety Analysis

All adverse events will be coded using the Medical Dictionary for Regulatory Activities (MedDRA). Each patient will be counted only once in each preferred term or system organ class (SOC) category for the analyses of safety. Summaries will be presented for all adverse events (overall and by severity), adverse events determined by the investigator to be related to study treatment (ie, reasonable possibility; see Section 7.1.4) (defined as related or with missing relationship) (overall and by severity), serious adverse events, and adverse events causing withdrawal from the study. Summaries will be presented by treatment group and for all patients. Patient listings of serious adverse events and adverse events leading to withdrawal will be presented.

Changes in laboratory and vital signs measurement data will be summarized descriptively. All values will be compared with prespecified boundaries to identify potentially clinically significant changes or values, and such values will be listed.

The use of concomitant medications will be summarized by therapeutic class using descriptive statistics. Concomitant medications will include all medications taken while the patient is treated with study drug.

For continuous variables, descriptive statistics (n, mean, standard deviation, standard error, median, minimum, and maximum) will be provided for actual values and changes from baseline to each time point. For categorical variables, patient counts and percentages will be provided. Descriptive summaries of serious adverse events, patient withdrawals due to adverse events, and potentially clinically significant abnormal values (clinical laboratory or vital signs) based on predefined criteria will also be provided.

If any patient dies during the study, a listing of deaths will be provided and all relevant information will be discussed in the patient narrative included in the clinical study report.

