11.1.2. Protocol Deviations

Any significant deviation from the protocol will be considered a protocol violation. Protocol violations include nonadherence on the part of the patient, the investigator, or the sponsor to protocol-specific inclusion/exclusion criteria, primary objective variable criteria, or GCP guidelines; noncompliance to study drug administration; use of prohibited medications; or any other deviations that may have an impact on the processes put in place for the care and safety of the patients. Protocol violations will be identified and recorded by investigational center personnel on the CRF. All protocol violations will be reported to the responsible IEC/IRB, as required.

When a protocol violation is reported, the sponsor will determine whether to discontinue the patient from the study or permit the patient to continue in the study, with documented approval from the medical representative. The decision will be based on ensuring the safety of the patient and preserving the integrity of the study.

Deviations from the inclusion/exclusion criteria of the protocol are not prospectively granted by the sponsor. If investigational center personnel learn that a patient who did not meet protocol eligibility criteria was entered into a study, they must immediately inform the sponsor of the protocol violation. If such patient has already completed the study or has withdrawn early, no action will be taken but the violation will be recorded.

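### Section 5.3.1 keeps patients who need an antipsychotic in the study, but section 7.1.7 as written would discontinue some of the same patients

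*Protocol*

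**What the plan says.** Section 1.7 gives the reason for the ban: "concomitant medications with antipsychotic drugs may confound the data due to side effects in the motor and cognitive domain". Section 5.3.1 puts antipsychotics on the list of drugs not allowed from 30 days before baseline to the end of the study. It then adds that patients who, in the treating physician's view, "are in need of antipsychotic medication or changed dose of antidepressant medication during the study, will be allowed to continue in the study", with the change entered on the CRF.

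Section 7.1.7 covers an adverse event that the investigator does not think warrants stopping but that "requires the use of a prohibited medication, thereby requiring discontinuation of the patient". It directs that the recorded reason be the need for the prohibited drug, not the adverse event. Section 4.3 lists 7.1.7 among the sections under which a patient may be withdrawn from the study.

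Section 11.1.2 counts use of prohibited medication as a protocol violation, after which "the sponsor will determine whether to discontinue the patient from the study or permit the patient to continue in the study".

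On analysis, section 9.6.2.1 states: "The model will include the following fixed effects: categorical week in trial by treatment interaction, center, and UHDRS-TMS at baseline". Section 9.6.2.4 reads: "No sensitivity analyses are planned for this study". Section 9.8.2 summarises concomitant medication by therapeutic class, with this limit: "Concomitant medications will include all medications taken while the patient is treated with study drug". The dates needed for more detail are collected. Section 5.3 covers medication up to the end of follow-up and says: "Indication, dosage, and start and end dates should be entered on the CRF".

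**The concern.** Two current sections give opposite outcomes for the same event, and neither refers to the other. What happens to a patient who develops, say, a behavioural crisis that needs an antipsychotic could depend on which section the site opens.

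Three things are at stake:

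- **Patient handling.** Someone whom the protocol means to keep could be withdrawn.
- **Data.** A patient withdrawn after Month 3 would have an early-termination evaluation in place of the Month 6 and Month 12 TMS and HD-CAB assessments. Missing data would then depend on how a site reads the protocol, in patients whose condition has probably worsened.
- **Tolerability counts.** Section 3.2.5 reports the proportion who discontinue, with reasons, and the proportion who discontinue because of adverse events. Under 5.3.1 this patient is in neither count. Under 7.1.7 the patient is in the first, with a reason other than the adverse event.

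**Working it through.** **Can one patient meet both rules?**

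1. An antipsychotic is a prohibited medication, because section 5.3.1 lists it as disallowed during the study.
2. The need for one can come from an adverse event. Section 7.1.1 counts new or worsening symptoms of the disease as an adverse event when they exceed what is expected for that patient.
3. Section 7.1.7 applies when such an event would not justify stopping by itself but calls for a prohibited drug. A psychiatric worsening treated with an antipsychotic fits.
4. Under 5.3.1 the patient continues. Under 7.1.7 the patient is discontinued.
5. The overlap is partial. If the need reflects expected disease course and is not an adverse event, 7.1.7 does not apply.

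**Does 7.1.7 mean study drug only?** Its opening sentences concern treatment. But the sentence at issue speaks of discontinuing the patient, the section requires Visit 8 procedures at the patient's withdrawal, and section 4.3 cites it as a route out of the study. The study-drug reading is possible but not secured.

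**Size for TMS.** Section 9.2 gives SD 6.2, a target of 2.5 points and about 100 patients per arm. The plan's figure reproduces: 2 × (1.960 + 0.842)² × 6.2² / 2.5² gives 97 per arm (two-sided 5%, 80% power), and power at 100 per arm is 81.4%. The standard error of the difference is 6.2 × √(2/100) = 0.877.

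Start rates and drug effects are not in the protocol, so everything below rests on assumed inputs.

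*Precision lost if patients are withdrawn and nothing is borrowed from earlier visits:*
- 5% of Month 12 values lost per arm: 6.2 × √(2/95) = 0.900, up 2.6%.
- 10% lost per arm: 6.2 × √(2/90) = 0.924, up 5.4%.

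*Shift in the observed arm difference if patients stay and are analysed as observed (either direction):*
- Starts differ by 10 percentage points, 6 points of TMS per starter: 0.10 × 6 = 0.60, which is 24% of 2.5 and 0.68 standard errors.
- Equal 10% starts, 6 points per starter, half the effect on laquinimod: 0.10 × 6 × 0.5 = 0.30, which is 12% of 2.5.
- Two starts per 100 against none: 0.02 × 6 = 0.12, about 5% of 2.5.
- Equal starts and equal drug effects: 0.

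No figure is offered for HD-CAB, because the protocol gives no SD for it.

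**Would an analysis setting post-start values to missing settle the matter?** In illustrative large-sample calculations (400,000 per arm, visit SDs 4.0 to 6.2, correlations 0.5 to 0.7, starts between Months 6 and 12), the error against the no-antipsychotic difference was:

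- under 0.01 points when starts followed observed Month 6 TMS, or when start rates were equal;
- 0.19 points (5% against 10% starts) and 0.43 points (0% against 10%) when starts followed unobserved Month 12 worsening. Varying the strength of that dependence gave 0.07 to 0.30 and 0.17 to 0.64.

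With 6 points per starter, the shifts under examination in those two cases are 0.05 × 6 = 0.30 and 0.10 × 6 = 0.60. The error can be about as large as the shift.

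**The case against.** The best reply is that 5.3.1 is a specific exception and should prevail over a general rule. The medication triggers in sections 3.6 and 4.3 name only moderate and strong CYP3A4 inhibitors. The 7.1.7 sentence mainly settles which reason to record, and can be read as covering only drugs that do force stopping. Section 3.6.2 also says early termination refers to study drug. Much of this stands: 5.3.1 is very probably what the sponsor intends. But 7.1.7 is not limited to CYP3A4 inhibitors and does not mention the exception.

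The gap in section 9.8.2 is also narrow. Antipsychotics are barred before baseline, so the on-treatment summary would show almost only starts. A start after the last dose should seldom precede an efficacy assessment, because the early-termination visit is due at or soon after that dose.

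Stronger readings are tempting, but the documents do not support them.

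- **Section 11.1.2 as a third conflicting rule.** It is not one. Recording a violation and permitting continuation is compatible with 5.3.1.
- **A biased primary analysis.** A reader might infer this from the missing term for starts and the statement in 9.6.2.4. Analysing patients as randomised, whatever medication they add, is valid. Arm differences produced by added medication are part of the effect it estimates.
- **A demonstrated drug interaction affecting the result.** Laquinimod induces CYP1A2 and Table 7 in Appendix C lists five antipsychotics among CYP1A2 substrates. But section 5.3.2.1 advises against such substrates, and nothing gives a size or direction for TMS.

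**Conclusion.** The point holds as a conflict between sections 5.3.1 and 7.1.7 for patients whose need for an antipsychotic arises from an adverse event. It is low in severity and does not invalidate the primary result. Its consequence is possible avoidable withdrawal, loss of later data and inconsistent discontinuation reasons.

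The number of patients affected is unknown and may be zero. Under the assumed inputs, the precision cost is about 3 to 5%, and the largest shift from starts analysed as observed is 0.60 points. With at most two starts per 100 in any arm it is 0.12 points, and a table of starts would be enough to close the question. The finding does not rest on these figures. It rests on the two sections' wording and on section 4.3 treating 7.1.7 as a route to withdrawal from the study.

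**What to change.** 1. In 7.1.7, state that the 5.3.1 exception for antipsychotics and changed antidepressant doses takes precedence, and that such patients are not discontinued for that reason. Add a cross-reference in 11.1.2.
2. Tabulate antipsychotic starts by arm with timing, including starts after study drug is stopped, which 9.8.2 leaves out.
3. Leave the as-randomised primary analysis as it is.
4. Optional, and only if starts are not rare: a supplementary repeated-measures analysis of TMS and HD-CAB with values after the first antipsychotic dose set to missing. Label it as a different, hypothetical estimand under an untestable missing-at-random assumption, and warn that it can be off by about as much as the shift it examines when starts differ by arm and follow worsening.

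Items 1 and 2 cost one sentence, one cross-reference and one table from dates already collected under section 5.3. Item 4 would cost one extra model and, on the assumptions above, 3 to 5% in standard error within that analysis.
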